7.5.6. Change from baseline to week 48 in T1-hypointense lesion volume

The change from baseline to week 48 in T1-hypointense lesion volume will be analyzed using the mITT1.

Since the change from baseline to week 48 in T1-hypointense volume might not follow normal distribution, the ranked values of this variable will be defined and analyzed using baseline-adjusted Analysis of Covariance (ANCOVA, SAS® PROC GLM) in which a contrast for comparing laquinimod 0.6 mg to placebo will be constructed. In addition to treatment group, natural logarithm of T1-hypointense lesion volume at baseline and CGR will be used as covariates. Due to the fact that the ANCOVA model will use ranked values and not the actual changes in the T1-hypointense volume, Hodges-Lehmann (HL) estimates will be used in order to present the magnitude of the treatment effect and the corresponding two-sided 95% confidence limit (i.e. p-values will be presented from the ANCOVA model and treatment effect with 95% confidence limits will be presented from the HL).

The SAS code for defining ranked values and performing this analysis is as follows:

1. Ranked values assignment:

```
PROC RANK OUT=RANKED;
  VAR CVOLT1 LVOLT1BASE;
  RANKS CVOLT1RANK LVOLT1BASERANK;
  WHERE ARM in ('Laquinimod 0.6 mg', 'Placebo');
  RUN;
```

2. ANCOVA model:

```
PROC GLM DATA=RANKED;
  CLASS ARM CGR;
  MODEL CVOLT1RANK = ARM LVOLT1BASERANK CGR /CLPARM SOLUTION;
```

```
LSMEANS ARM /STDERR CL;
ESTIMATE 'Laq 0.6 to Plb' ARM 1 -1;
RUN;
```

3. HL estimates:

```
PROC NPAR1WAY HL;
CLASS ARM;
VAR CVOLT1;
WHERE ARM in ('Laquinimod 0.6 mg', 'Placebo');
RUN;
```

In addition, T1-hypointence lesion volume and change from baseline to week 48 will be summarized using descriptive statistics.

7.5.7. Change from baseline to week 48 in T2 lesion volume

The change from baseline to week 48 in T2 lesion volume will be analyzed by applying the same methodology used to analyze the change from baseline to week 48 in T1-hypointence lesion volume (see Section 7.5.6). Natural logarithm of baseline T1-hypointense lesion volume covariate will be replaced by natural logarithm of baseline T2 lesion volume. In addition, T2 lesion volume and change from baseline to week 48 will be summarized using descriptive statistics.

7.5.8. Normalized Thalamic Volume percent change from baseline to week 48

Normalized thalamic volume percent change from baseline to week 48 will be calculated as change from baseline to week 48 in the normalized thalamic volume divided by normalized thalamic volume at baseline. In cases when a patient performs early termination, scan under at least 36 weeks of treatment will be used in this derivation (as specified in Section 5.5). This variable will be analyzed using the mITT1 population. This analysis will be performed using baseline-adjusted Analysis of Covariance (ANCOVA, SAS® PROC GLM) in which a contrast for comparing laquinimod 0.6 mg to placebo will be constructed. In addition to treatment group, normalized thalamic volume at baseline and CGR will be used as covariates. The SAS code for this analysis is as follows:

```
PROC GLM;
CLASS ARM CGR;
MODEL NTHALVOL = ARM BTHALVOL CGR /CLPARM SOLUTION;
LSMEANS ARM /STDERR CL;
ESTIMATE 'Laq 0.6 to Plb' ARM 1 -1;
WHERE ARM in ('Laquinimod 0.6 mg', 'Placebo');
RUN;
```

In addition, the normalized thalamic volume percent change from baseline to week 48 will be summarized using descriptive statistics.

7.5.9. Mean Cortical Thickness percent change from baseline to week 48

The mean cortical thickness percent change from baseline to week 48 will be derived and analyzed by applying the same methodology used to define and analyze the normalized thalamic

volume percent change from baseline to week 48 (see Section 7.5.8). Baseline normalized thalamic volume mean covariate will be replaced by cortical thickness at baseline. In addition, the mean cortical thickness percent change from baseline to week 48 will be summarized using descriptive statistics.

7.5.10. Normalized White Matter Volume percent change from baseline to week 48

The normalized white matter volume percent change from baseline to week 48 will be derived and analyzed by applying the same methodology used to define and analyze the normalized thalamic volume percent change from baseline to at week 48 (see Section 7.5.8). Baseline normalized thalamic volume mean covariate will be replaced by normalized white matter volume at baseline. In addition, normalized white matter volume percent change from baseline to at week 48 will be summarized using descriptive statistics.

7.5.11. Mean Upper Cervical Cord Area percent change from baseline to week 48

The mean upper cervical cord area percent change from baseline to week 48 will be derived and analyzed by applying the same methodology used to define and analyze the normalized thalamic volume percent change from baseline to at week 48 (see Section 7.5.8). Baseline normalized thalamic volume mean covariate will be replaced by mean upper cervical cord area at baseline. In addition, mean upper cervical cord area percent change from baseline to at week 48 will be summarized using descriptive statistics.

7.5.12. Number of T2 Cervical Cord Lesions at week 48

The number of T2 cervical cord lesions at week 48 will be analyzed by applying the same methodology used to analyze the number of new T2 lesions at week 48 (see Section 7.4.4). Natural logarithm of T2 lesion volume at baseline covariate will be replaced by number of T2 cervical cord lesions at baseline. In addition, the number of T2 cervical cord lesions at week 48 will be summarized using descriptive statistics.

7.5.13. Mean MTR Normal-Appearing Brain Tissue (NABT) percent change from baseline to week 48

The MTR NABT percent change from baseline to week 48 will be derived and analyzed by applying the same methodology used to define and analyze the normalized thalamic volume percent change from baseline to at week 48 (see Section 7.5.8). Baseline normalized thalamic volume mean covariate will be replaced by MTR NABT at baseline. In addition, MTR NABT percent change from baseline to at week 48 will be summarized using descriptive statistics.

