### 6.4.1. MRI Evaluations

The patients will undergo up to 3 MRI scans:

- baseline (at least 14 days but not more than 6 weeks prior to baseline)
- week 24
- week 48 (or ET visit if performed after the week 36 visit and prior to week 48).

Gd will be administered at baseline MRI only. In case of steroid treatment, study MRI should be performed before or be delayed to allow a minimum of 14 days, but not more than 28 days, from the completion of the steroid course.

The following parameters will be assessed:

- normalized brain volume - at baseline
- PBVC – at week 24 as well as week 48 or ET
- T2-lesions volume – at baseline, as well as week 48 or ET
- T1 hypointense lesions volume - at baseline, as well as week 48 or ET
- number of GdE-T1 lesions – at baseline
- number of new T2 lesions - at week 48 or ET
- number of new T1 hypointense lesions - at week 48 or ET
- thalamic volume, cortical volume, and white matter volume - at baseline
- percent volume change (thalamus, cortex, white matter) - at week 48 or ET
- normalized cervical cord area based on 3D T1-w acquisition of the cervical cord - at baseline
- cervical cord area percentage volume change - at week 48 or ET
- number of T2 cervical cord lesions based on a sagittal T2 acquisition of the cervical cord - at baseline
- number of new T2 cervical cord lesions based on a sagittal T2 acquisition of the cervical cord - at week 48 or ET
- normal-appearing brain tissue average MTR, at baseline, as well as week 48 or ET

If MTR is not performed due to MRI site technical limitations, this would not be considered a protocol violation.

Additional details of MRI procedures are presented in [Appendix F](#) and in the MRI manual.

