12. CHANGES TO PROTOCOL SPECIFIED ANALYSES

The following changes to protocol specified analyses are introduced in this SAP:

- Multiplicity adjustment at alpha level of 5% was added for the analyses of the primary and secondary endpoints.
- Sensitivity analyses for primary and secondary endpoints which use data recorded after patient early terminates treatment and continues to come to the follow up visits were removed.

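### SAP 7.5.12 models all cervical cord T2 lesions at week 48 instead of new ones, which dilutes any effect on new lesions in this exploratory endpoint

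*SAP*

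**What the plan says.** **Protocol 6.4.1** lists the MRI parameters by visit. For the cervical cord, the baseline reading is the "number of T2 cervical cord lesions based on a sagittal T2 acquisition of the cervical cord - at baseline" and the follow-up reading is the "number of new T2 cervical cord lesions based on a sagittal T2 acquisition of the cervical cord - at week 48 or ET". No total cord count is listed at week 48. For the cortex, the baseline reading comes from "thalamic volume, cortical volume, and white matter volume - at baseline" and the follow-up reading from "percent volume change (thalamus, cortex, white matter) - at week 48 or ET". Cortical thickness is not listed at any visit.

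**SAP 7.5.12** says: "The number of T2 cervical cord lesions at week 48 will be analyzed by applying the same methodology" as for new T2 lesions in SAP 7.4.4, a log-link negative binomial regression. The baseline number of cord T2 lesions replaces the log of baseline T2 lesion volume as covariate. The titles of SAP summary tables 15.57 and 15.58 also omit the word new, whereas tables 15.31 (brain T2) and 15.43 (T1-hypointense) include it.

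**SAP 7.5.9** says: "The mean cortical thickness percent change from baseline to week 48 will be derived and analyzed" in the same way as thalamic volume.

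The exploratory endpoint lists (protocol synopsis, 3.2.3 and 9.6.3; SAP 3.2.3) name the number of cervical cord T2 lesions without the word new, and cortical atrophy without a metric.

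**The concern.** The model in SAP 7.4.4 was written for lesions that appear on treatment. SAP 7.5.12 applies it to a count that, read literally, includes every cord lesion the patient already had at randomisation. Treatment cannot have prevented those lesions, and they enter both arms equally, so the rate ratio is pulled towards 1. Putting the raw baseline count in the model does not undo this. Under a log link the covariate acts multiplicatively, whereas the outcome is roughly baseline plus new lesions, which is additive.

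At stake is one exploratory readout of cord disease activity. A rate ratio close to 1 could be read as no effect on the cord when the chosen variable was unable to show much. The cortical point is smaller: the plan analyses a metric that the protocol's measurement list does not contain, and gives no reason.

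**Working it through.** **1. The plan's own figure.** The documents give no power or sample size for cord lesions. The only stated power is 84% for PBVC with 126 per arm, difference 0.3 and SD 0.8 (protocol 9.2). Check: standard error = 0.8 × √(2/126) = 0.1008; 0.3/0.1008 = 2.976; power = Φ(2.976 − 1.960) = Φ(1.016) = 84.5%, which agrees. Likewise 252/0.9 = 280, as stated. Only the 126 per arm is carried forward.

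**2. The variables side by side.**

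| Item | Protocol 6.4.1, baseline | Protocol 6.4.1, week 48 or ET | SAP variable at week 48 |
|---|---|---|---|
| Cord T2 lesions | total count | new lesions | number, not restricted to new (7.5.12) |
| Brain T2 lesions | lesion volume | new lesions; lesion volume | new lesions (7.4.4) |
| T1-hypointense lesions | lesion volume | new lesions; lesion volume | new lesions (7.5.5) |
| Cortex | volume | percent volume change | thickness percent change (7.5.9) |

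Where 6.4.1 wants the same reading at both visits it says so, as it does for T2 volume, T1-hypointense volume and MTR. The cord total is not among these.

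**3. Expected rate ratio on the total.** Let B be the mean baseline cord count, m the mean number of new lesions on placebo, and r the true rate ratio for new lesions. If no lesion resolves,

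RR(total) = (B + r·m)/(B + m) = 1 − (1 − r)·m/(B + m).

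Take r = 0.70. This borrows the 30% reduction in new T2 lesions in protocol Table 1, from brain scans in a relapsing-remitting trial; carrying it to the cord in PPMS is an assumption. B and m are assumptions too.

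| B | m = 0.1 | m = 0.3 | m = 1.0 |
|---|---|---|---|
| 1 | 0.973 | 0.931 | 0.850 |
| 2 | 0.986 | 0.961 | 0.900 |
| 4 | 0.993 | 0.979 | 0.940 |
| 6 | 0.995 | 0.986 | 0.957 |

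Extremes: (1 + 0.7)/(1 + 1) = 0.850, a 15% reduction; (6 + 0.07)/(6 + 0.1) = 0.995, a 0.5% reduction.

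**4. Simulated power.** 126 per arm, 400 runs per scenario, r = 0.70, overdispersed baseline and new counts drawn independently. The model was negative binomial with arm and baseline cord count (Poisson where the negative binomial did not fit), tested two-sided at 5%. Age and country/region were left out.

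| B | m | New: rate ratio, power | Total: rate ratio, power |
|---|---|---|---|
| 2 | 0.3 | 0.695, 24% | 0.958, 3% |
| 2 | 1.0 | 0.696, 49% | 0.892, 32% |
| 4 | 0.3 | 0.687, 27% | 0.978, 4% |
| 4 | 1.0 | 0.696, 49% | 0.938, 18% |

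The Monte Carlo standard error is at most √(0.25/400) = 2.5 percentage points.

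**5. Cortex.** No arithmetic applies. Cortical thickness cannot be obtained from any reading listed in 6.4.1, and the documents give no figure for comparing thickness with volume.

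**The case against.** The strongest reply is that the SAP follows the protocol's named endpoint. The endpoint lists omit new for cord lesions while including it for the neighbouring T1-hypointense item, and SAP 3.2.3 repeats them. This stands: the conflict lies inside the protocol, between its endpoint lists and 6.4.1, and the SAP sides with one of the two. It does not make the total a good outcome, and the two places still need to be reconciled.

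Second, the wording may be shorthand for new lesions, since 7.5.12 borrows the new-lesion model. That is possible. But the table titles keep the distinction elsewhere, and a programmer following the text would analyse the total.

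Third, silence in SAP Section 12 ("The following changes to protocol specified analyses are introduced in this SAP") proves little. Protocol 9.6.4.4 leaves exploratory methods to the SAP, and the SAP preface says differences from the protocol will be explained in the study report. This also stands for the choice of method. It does not tell the reader why cortical volume became cortical thickness.

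Fourth, lesion frequency is unknown. If new cord lesions were frequent relative to baseline, the loss would be smaller, which is why a range is shown.

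**Conclusion.** The point holds for the cord lesion count. Followed as written, SAP 7.5.12 shrinks a true 30% reduction in new lesions to about 0.5% to 15% over the assumed range, and lowers power from 24-49% to 3-32% in the scenarios simulated. The direction depends only on baseline lesions persisting; the size depends on B and m, which the documents do not give. Even on new lesions the analysis is not well powered. The cortical mismatch is a reconciliation item with no size attached.

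Stronger conclusions that a reader might infer are not supported:

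- *That thalamic volume, white matter volume and cord area are also diluted or made noisier.* SAP 7.5.8 defines its variable as "calculated as change from baseline to week 48 in the normalized thalamic volume divided by normalized thalamic volume at baseline", which is itself a percent volume change; 7.5.10 and 7.5.11 follow it. Protocol 6.4.1 gives no method for its percent change, and neither document gives a measurement error, so no loss is shown.
- *That the SAP variables cannot be derived.* Among the listed readings, only cortical thickness has no source. A week-48 cord total follows from baseline plus new lesions if none resolves. The MRI manual, which is not among the documents, may list further outputs.
- *That the total count can never show an effect.* Power reached 32% in one scenario.
- *That the trial's main conclusions are at risk.* These variables are exploratory and outside the testing hierarchy in SAP 5.3.

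**What to change.** - **SAP 7.5.12 and tables 15.57-15.58:** make the outcome the number of new cervical cord T2 lesions at week 48, analysed with the 7.4.4 model, keeping the baseline cord lesion count as covariate.
- **Endpoint lists (protocol synopsis, 3.2.3, 9.6.3; SAP 3.2.3):** insert the word new so that they agree with protocol 6.4.1.
- **SAP 7.5.9:** analyse the cortical percent volume change listed in 6.4.1, or keep thickness and record the departure and its reason in SAP Section 12.

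The cost is wording, two table titles and some reprogramming. Protocol 6.4.1 already lists the new cord count and the cortical percent volume change, so no additional scan or reading is needed for either.

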7.5.14. Change from baseline to week 48 in 9-Hole Peg Test (9HPT)

The change from baseline to week 48 in the 9HPT test will be analyzed using the same methodology as described for the change from baseline to week 48 in the T25FW test in Section 7.4.3. Baseline T25FW covariate will be replaced by baseline 9HPT test.

In addition, actual values of the 9HPT and changes from baseline to each week will be summarized using descriptive statistics.

When the study is completed, actual values of 9HPT and changes from baseline to each visit will be summarized using descriptive statistics to include both part A and part B. Also, the changes

from baseline to each visit will be analyzed using similar statistical methodology as presented in this section for changes from baseline to week 48 in 9HPT test.

7.5.15. Change from baseline to week 48 in Symbol Digit Modalities Test (SDMT)

Change from baseline to week 48 in SDMT score will be analyzed for mITT2 population using baseline adjusted repeated measures analysis of covariance (ANCOVA SAS® PROC MIXED) in which 1 contrast will be constructed in order to compare between laquinimod 0.6 mg and placebo. The model will be comprised from the treatment group as a class variable (2 levels). In addition to the treatment group, week (categorical, 4 levels), treatment by week interaction, SDMT at baseline, and CGR will be used as covariates. Additionally, week (categorical) will be specified as a repeated effect and unstructured (UN) correlation matrix will be used to model intra-subject correlation. In case a convergence issue will arise using the UN correlation matrix, (1) AR1 or (2) Compound Symmetry (CS) will be used to enable model convergence (in this order). The SAS code for this analysis is as follows:

```
PROC MIXED;
  CLASS SUBJID ARM WEEK CGR;
  MODEL CSDMT=ARM WEEK ARM*WEEK SDMTBASE CGR / SOLUTION CL;
  REPEATED WEEK / TYPE=UN SUBJECT=SUBJID R RCORR;
  ESTIMATE 'Laq 0.6 to Plb' ARM 1 -1 ARM*WEEK 0 0 0 1 0 0 0 -1 / CL;
  LSMEANS ARM*WEEK / PDIFF CL;
  WHERE ARM in ('Laquinimod 0.6 mg', 'Placebo');
RUN;
```

In addition, actual values of the SDMT score and changes from baseline to each visit will be summarized using descriptive statistics.

When the study is completed, actual values of SDMT and changes from baseline to each visit will be summarized using descriptive statistics to include both part A and part B. Also, the changes from baseline to each visit will be analyzed using similar statistical methodology as presented in this section for changes from baseline to week 48 in SDMT test.

7.5.16. Change from baseline to week 48 in Low Contrast Visual Acuity (LCVA)

The changes from baseline to week 48 in LCVA will be analyzed for each chart type (100%, 2.5% and 1.25%) separately while using binocular values.

These analyses will be performed using the same methods as described for the primary efficacy variable in Section 7.2 and mITT2 population will be used. The age at baseline will also be included in the model. Baseline brain volume will be replaced by baseline LCVA.

In addition, actual values of LCVA and changes from baseline to each visit will be summarized using descriptive statistics.

When the study is completed, actual values of LCVA and changes from baseline to each visit will be summarized using descriptive statistics to include both part A and part B. Also, the changes from baseline to each visit will be analyzed using similar statistical methodology as presented in this section for changes from baseline to week 48 in LCVA test.

7.5.17. Change from baseline to week 48 in 12-Item Multiple Sclerosis Walking Scale (MSWS-12)

The change from baseline to week 48 in the MSWS-12 score will be analyzed using the same methodology as described for the change from baseline to week 48 in the SDMT score in Section 7.5.15. Baseline SDMT covariate will be replaced by baseline MSWS-12.

In addition, actual values of the MSWS-12 score and changes from baseline to each visit will be summarized using descriptive statistics.

When the study is completed, actual values of MSWS-12 and changes from baseline to each visit will be summarized using descriptive statistics to include both part A and part B. Also, the changes from baseline to each visit will be analyzed using similar statistical methodology as presented in this section for changes from baseline to week 48 in MSWS-12 test.

7.5.18. Relapses

Two types of relapses will be presented using descriptive statistics for relapsing and relapse-free patients:

1. Clinical relapse as captured by the clinical database.
2. Protocol defined relapse. In order to identify protocol defined relapses, all clinical relapses will be cross checked with EDSS evaluation data performed during the clinical relapse, i.e. between the onset and the stabilization date of the relapse. If several EDSS evaluations are available during relapse, then the closest evaluation to the relapse onset will be taken. A clinical relapse will be considered as protocol defined if one of the following conditions holds:
 - an increase of at least 0.5 in the EDSS score as compared to previous the evaluation
 - an increase of 1 grade in the score of 2 or more of the 7 functions from the FSS as compared to the previous evaluation
 - an increase of 2 grades in the score of 1 function from the FSS as compared to the previous evaluation

When the study is completed, the tables of clinical and protocol defined relapses will be generated again to include both part A and part B.

7.5.19. mRS at week 72

mRS at week 72 will be presented for mITT2 population as both continuous and categorical variable using descriptive statistics. This analysis will be repeated to include both part A and part B when the study is completed.

7.5.20. Time to CDP event as measured by T25FW

Time to CDP as measured by T25FW will be defined as an increase of at least 20% from baseline in T25FW test (see Section 7.4.3 for definition), confirmed after at least 12 weeks. Progression cannot be confirmed during a protocol defined relapse.

Similar algorithm to that described for CDP as measured by EDSS confirmed after at least 12 weeks will be used for definition and censoring rules of this variable (see Section 7.4.1).

Time to CDP as measured by T25FW for each individual will be analyzed using the same methods as described for time to CDP as measured by EDSS in Section 7.4.1. In addition to treatment group, T25FW at baseline and CGR will be used as covariates.

In case the above model will not converge due to CGR variable, then CGR will be removed from the model.

The adequacy of the proportional hazards assumption will be checked using the same methodology as described for time to CDP as measured by EDSS in Section 7.4.1.

In addition, patients with CDP as measured by T25FW will be summarized using descriptive statistics. The time to CDP as measured by T25FW will be presented by Kaplan-Meier curves stratified by treatment group.

All analyses presented in the section will be repeated to include both part A and part B when the study is completed.

